### Contraception Guidance

#### Male participants

- Male participants with female partners of child-bearing potential are eligible to participate if they agree to ONE of the following during the protocol-defined time frame in Section 6.1:
  - Are abstinent from penile-vaginal intercourse as their usual and preferred lifestyle (abstinent on a long term and persistent basis) and agree to remain abstinent

- Agree to use a male condom plus an additional method of contraception with a failure rate of <1% per year as described in [Table 5](#) when having penile-vaginal intercourse with a woman of childbearing potential
- Men with a pregnant or breastfeeding partner must agree to remain abstinent from penile-vaginal intercourse or use a male condom during each episode of penile penetration during the protocol-defined time frame.
- In addition, male participants must refrain from donating sperm for duration of study and for at least 10 days after the last dose.

**Table 5      Highly Effective Contraceptive Methods**

Highly Effective Contraceptive Methods That Are User Dependent a Failure rate of <1% per year when used consistently and correctly.	
Combined (estrogen- and progestogen-containing) hormonal contraception associated with inhibition of ovulation 
 
• oral
 
• intravaginal
 
• transdermal
 
	
Progestogen-only hormonal contraception associated with inhibition of ovulation 
 
• injectable
 
	
Highly Effective Methods That Are User Independent	

 
• Implantable progestogen-only hormonal contraception associated with inhibition of ovulation
 
• Intrauterine device (IUD)
 
• Intrauterine hormone-releasing system (IUS)
 
• bilateral tubal occlusion / ligation
 
	
Vasectomized partner (A vasectomized partner is a highly effective contraception method provided that the partner is the sole male sexual partner of the WOCBP and the absence of sperm has been confirmed. If not, an additional highly effective method of contraception should be used.)	
Sexual abstinence (Sexual abstinence is considered a highly effective method only if defined as refraining from heterosexual intercourse during the entire period of risk associated with the study drug. The reliability of sexual abstinence needs to be evaluated in relation to the duration of the study and the preferred and usual lifestyle of the participant.)	

NOTES:

a. Typical use failure rates may differ from those when used consistently and correctly. Use should be consistent with local regulations regarding the use of contraceptive methods for participants in clinical studies.

## Collection of Pregnancy Information

### Male participants with partners who become pregnant

- Investigator will attempt to collect pregnancy information on any male participant's female partner of a male study participant who becomes pregnant while participating in this study. This applies only to participants who receive study treatment.
- After obtaining the necessary signed informed consent from the pregnant female partner directly, the investigator will record pregnancy information on the appropriate form and submit it to GSK within 24 hours of learning of the partner's pregnancy.
- Partner will also be followed to determine the outcome of the pregnancy. Information on the status of the mother and child will be forwarded to GSK
- Generally, follow-up will be no longer than 6 to 8 weeks following the estimated delivery date. Any termination of the pregnancy will be reported regardless of fetal status (presence or absence of anomalies) or indication for procedure.

## 12.6. Appendix 6: Liver Safety: Required Actions and Follow-up Assessments

### Phase I liver chemistry stopping criteria and required follow up assessments

Liver Chemistry Stopping Criteria	
Required Actions and Follow up Assessments	
Actions	Follow Up Assessments

ALT-absolute
 
ALT<math>\geq</math>3xULN
 
If ALT<math>\geq</math>3xULN AND bilirubin <math>\geq</math>2xULN (>35% direct bilirubin) or INR <math>></math>1.5, Report as an SAE.
 
See additional Actions and Follow Up Assessments listed below
	
 
• Immediately discontinue study treatment
 
• Report the event to GSK within 24 hours
 
• Complete the liver event CRF, and complete an SAE data collection tool if the event also meets the criteria for an SAE
 
• Perform liver event follow up assessments
 
• Monitor the subject until liver chemistries resolve, stabilise, or return to within baseline (see MONITORING below)
 
 
MONITORING:
 
If ALT<math>\geq</math>3xULN AND bilirubin <math>\geq</math> 2xULN or INR <math>></math>1.5
 
 
• Repeat liver chemistries (include ALT, AST, alkaline phosphatase, bilirubin) and perform liver event follow up assessments within 24 hrs
 
• Monitor subjects twice weekly until liver chemistries resolve, stabilise or return to within baseline
 
• A specialist or hepatology consultation is recommended
 
 
If ALT<math>\geq</math>3xULN AND bilirubin <math><</math>2xULN and INR <math>\leq</math>1.5:
 
 
• Repeat liver chemistries (include ALT, AST, alkaline phosphatase, bilirubin) and perform
 
 
 
• Viral hepatitis serology
 
• Obtain INR and recheck with each liver chemistry assessment until the transaminases values show downward trend
 
• Obtain blood sample for pharmacokinetic (PK) analysis, obtained within 7 days of last dose
 
• Serum creatine phosphokinase (CPK) and lactate dehydrogenase (LDH).
 
• Fractionate bilirubin, if total bilirubin<math>\geq</math>2xULN
 
• Obtain complete blood count with differential to assess eosinophilia
 
• Record the appearance or worsening of clinical symptoms of liver injury, or hypersensitivity, on the AE report form
 
• Record use of concomitant medications on the concomitant medications report form including acetaminophen, herbal remedies, other over the counter medications.
 
• Record alcohol use on the liver event alcohol intake case report form
 
 
If ALT<math>\geq</math>3xULN AND bilirubin <math>\geq</math>2xULN or INR <math>></math>1.5:
 
 
• Anti-nuclear antibody, anti-smooth muscle
 


Liver Chemistry Stopping Criteria	

liver event follow up assessments within 24-72 hrs
 
 
Monitor subjects weekly until liver chemistries resolve, stabilize or return to within baseline
 
	
antibody, Type 1 anti-liver kidney microsomal antibodies, and quantitative total immunoglobulin G (IgG) or gamma globulins.
 
 
Serum acetaminophen adduct high performance liquid chromatography (HPLC) assay (quantifies potential acetaminophen contribution to liver injury in subjects with definite or likely acetaminophen use in the preceding week [James, 2009].
 
Liver imaging (ultrasound, magnetic resonance, or computerised tomography) and /or liver biopsy to evaluate liver disease; complete Liver Imaging and/or Liver Biopsy CRF forms.
 

1. Serum bilirubin fractionation should be performed if testing is available. If serum bilirubin fractionation is not immediately available, discontinue study treatment for that subject if ALT  $\geq 3 \times \text{ULN}$  and bilirubin  $\geq 2 \times \text{ULN}$ . Additionally, if serum bilirubin fractionation testing is unavailable, record presence of detectable urinary bilirubin on dipstick, indicating direct bilirubin elevations and suggesting liver injury.
2. All events of ALT  $\geq 3 \times \text{ULN}$  and bilirubin  $\geq 2 \times \text{ULN}$  ( $>35\%$  direct bilirubin) or ALT  $\geq 3 \times \text{ULN}$  and INR  $> 1.5$ , if INR measured, which may indicate severe liver injury (possible 'Hy's Law'), must be reported as an SAE (excluding studies of hepatic impairment or cirrhosis); INR measurement is not required and the threshold value stated will not apply to subjects receiving anticoagulants
3. Includes: Hepatitis A IgM antibody; Hepatitis B surface antigen and Hepatitis B Core Antibody (IgM); Hepatitis C RNA; Cytomegalovirus IgM antibody; Epstein-Barr viral capsid antigen IgM antibody (or if unavailable, obtain heterophile antibody or monospot testing); Hepatitis E IgM antibody
4. PK sample may not be required for subjects known to be receiving placebo or non-GSK comparator treatments. Record the date/time of the PK blood sample draw and the date/time of the last dose of study treatment prior to PK blood sample draw on the CRF. If the date or time of the last dose is unclear, provide the subject's best approximation. If the date/time of the last dose cannot be approximated OR a PK sample cannot be collected in the time period indicated above, do not obtain a PK sample. Instructions for sample handling and shipping are in the SRM.

1. INTRODUCTION

The purpose of this reporting and analysis plan (RAP) is to describe the analyses to be included in the Clinical Study Report for Protocol 206874:

Revision Chronology:		
2017N347248_00	12-DEC-2017	Original

2. SUMMARY OF KEY PROTOCOL INFORMATION

2.1. Changes to the Protocol Defined Statistical Analysis Plan

There were no changes or deviations to the originally planned statistical analysis specified in the protocol (Dated: 12/DEC/2017).

2.2. Study Objective(s) and Endpoint(s)

Objectives	Endpoints
Primary Objectives	Primary Endpoints

 To characterize the effect of repeat oral dosing of itraconazole on the pharmacokinetics of a single inhaled dose of GSK2269557 (nemralisib) in healthy subjects. 	
 AUC(0-∞) AUC(0-t) Cmax Tmax t_{1/2}
Secondary Objectives	Secondary Endpoints

 To investigate the safety and tolerability of single inhaled dose of nemralisib, when dosed alone and concomitantly with itraconazole, in healthy subjects. 	
 Adverse events (AE), Clinical laboratory values, Vital signs, Electrocardiogram (ECG) and Spirometry.

 To investigate the pharmacokinetics of itraconazole and hydroxy itraconazole when co-administered with nemralisib. 	
 AUC(0-∞) AUC(0-t) Cmax tmax t_{1/2}

AUC(0-∞) Area under the concentration-time curve from time zero (pre-dose) extrapolated to infinite time, AUC(0-t): Area under the plasma concentration versus time curve from time zero to t, Cmax: maximum observed plasma concentration, tmax: time to Cmax, t_{1/2}: Terminal phase half-life.

2.3. Study Design

Overview of Study Design and Key Features	
Design Features	
 One sequence crossover, open label, single centre. There will be a washout of at least 14 days between the administration of nemiralisib in Period 1 and the administration of nemiralisib in Period 2. Subjects will be admitted to the clinical research unit on Day -1 and will remain in-house until collection of the final PK sample in each period. The final PK sample will be Day 6 in Period 1 and Day 11 in Period 2.
Dosing	
 Period 1, nemiralisib: On Day 1, subjects will receive a single dose of 100 mcg nemiralisib. Period 2, itraconazole: From Day 1 to 10 inclusive, subjects will receive a single dose of 200 mg itraconazole in the morning Period 2, nemiralisib: On Day 5, subjects will receive a single dose of 100 mcg nemiralisib one hour after the dose of 200 mg itraconazole. Participants will receive the administration of nemiralisib on Day 5 and itraconazole doses on Day 5 to Day 10 only if there are no findings that are considered clinically significant by the Investigator (in consultation with the medical monitor if needed) during review of Day 4 clinical chemistry and ECG.
Time & Events	
 Refer to Appendix 1: Schedule of Activities.
Treatment Assignment	
 All subjects will receive the same treatments in the same periods/on the same study days.
Interim Analysis	
 A preliminary assessment of PK will be performed following the availability of the PK data, for internal decision making.

2.4. Statistical Hypotheses / Statistical Analyses

This study is designed to characterise the effect of repeat oral dosing of itraconazole on the pharmacokinetics of a single inhaled dose of nemiralisib in healthy participants. In particular, a comparison will be made between:

- The exposure of nemiralisib administered alone and the exposure of nemiralisib co-administered following repeat doses of itraconazole.

For AUC(0-∞) and Cmax, point estimates and corresponding two-sided 90% confidence intervals (CIs) will be constructed for the ratio of the geometric means. No formal hypotheses will be tested.

3. PLANNED ANALYSES

3.1. Interim Analyses

Following the availability of PK data prior to DBF, a preliminary assessment of unblinded PK data will be performed by CPMS using nominal timepoints. This assessment will be for internal decision making only, will not be formally reported and SAC deliverables will supersede any such output.

3.2. Final Analyses

The final planned primary analyses will be performed after the completion of the following sequential steps:

1. All participants have completed the study as defined in the protocol.
2. All required database cleaning activities have been completed and final database release (DBR) and database freeze (DBF) has been declared by Data Management.

4. ANALYSIS POPULATIONS

Population	Definition / Criteria	Analyses Evaluated
Screened	
• All participants screened and for whom a record exists on the study database.	
• Screening Status/Screening Failures
Enrolled	
• All participants who passed screening and entered the study. Included are: run-in failures; and participants who took treatment.• Note screening failures and participants screened but never enrolled into the study are excluded from the Enrolled population as they did not enter the study.	
• Summary of Study Populations• Summary of Age Ranges
Safety	
• All participants enrolled in the study, who took at least one dose of study treatment.• Participants will be analysed according to the treatment they actually received.• Note: Participants who were not assigned treatment but received at least one dose of study treatment should be listed.	
• Other Study Population• Safety
Pharmacokinetic (PK)	
• All participants enrolled in the study who took at least 1 dose of nemralisib and for whom a nemralisib pharmacokinetic sample was obtained and analysed.• Participants will be analysed according to the treatment they received.	
• PK

Refer to [Appendix 8](#): List of Data Displays which details the population used for each display.

4.1. Protocol Deviations

Important protocol deviations (including deviations related to study inclusion/exclusion criteria, conduct of the trial, patient management or patient assessment) will be summarised and listed.

Protocol deviations will be tracked by the study team throughout the conduct of the study in accordance with the Protocol Deviation Management Plan.

- Data will be reviewed prior to freezing the database to ensure all important deviations are captured and categorised in the protocol deviations dataset.
- This dataset will be the basis for the summaries and listings of protocol deviations.

A separate summary and listing of all inclusion/exclusion criteria deviations will also be provided. This summary will be based on data as recorded on the inclusion/exclusion page of the eCRF.

5. CONSIDERATIONS FOR DATA ANALYSES AND DATA HANDLING CONVENTIONS

5.1. Study Treatment & Sub-group Display Descriptors

Treatment Group Descriptions	
Data Displays for Reporting	
Description	Order in TLF
NEMI 100mcg SD Alone	1
NEMI 100mcg SD with Itraconazole 200mg RD	2

Treatment comparisons will be displayed using the descriptors as follows:

- NEMI 100mcg SD with Itraconazole 200mg RD vs. NEMI 100mcg SD Alone

5.2. Baseline Definitions

For all endpoints (except as noted in baseline definitions below) the baseline value will be the latest pre-dose assessment with a non-missing value, for the relevant period, including those from unscheduled visits. If time is not collected, Day 1 assessments are assumed to be taken prior to first dose and used as baseline. Note that baseline for FEV1 is defined as the screening visit in the protocol; however it is not required in any data displays so is not included here.

Parameter	Study Assessments Considered as Baseline		Baseline Used in Data Display
	Screening	Day 1 (Pre-Dose) [Periods 1 and 2]	
Safety			
Vital Signs	X ¹	X	Day 1 predose for the relevant period
ECG	X ¹	X	Day 1 predose for the relevant period

[1] Triplicate

Unless otherwise stated, if baseline data is missing no derivation will be performed and baseline will be set to missing.

5.3. Multiple Comparisons and Multiplicity

No adjustments for multiplicity will be made.

5.4. Other Considerations for Data Analyses and Data Handling Conventions

Other considerations for data analyses and data handling conventions are outlined in the following appendices:

Section	Component
11.2	Appendix 2: Study Phases and Treatment Emergent Adverse Events
11.3	Appendix 3: Data Display Standards & Handling Conventions
11.4	Appendix 4: Derived and Transformed Data
11.5	Appendix 5: Reporting Standards for Missing Data
11.6	Appendix 6: Values of Potential Clinical Importance

6. STUDY POPULATION ANALYSES

6.1. Overview of Planned Study Population Analyses

The study population analyses will be based on the “Safety” population, unless otherwise specified.

Study population analyses including analyses of subject’s disposition, protocol deviations, demographic and baseline characteristics, prior and concomitant medications, and exposure will be based on GSK Core Data Standards. Details of the planned displays are presented in [Appendix 8: List of Data Displays](#).

7. PHARMACOKINETIC ANALYSES

7.1. Primary Pharmacokinetic Analyses

7.1.1. Endpoint / Variables

7.1.1.1. Drug Concentration Measures

Nemralisib drug concentration data will be displayed as detailed in [Appendix 3: Data Display Standards & Handling Conventions](#) (Section [11.3.3 Reporting Standards for Pharmacokinetic](#)).

7.1.1.2. Derived Pharmacokinetic Parameters

Nemralisib pharmacokinetic parameters will be calculated by standard non-compartmental analysis according to current working practices and using the currently supported version of WinNonlin. All calculations of non-compartmental parameters will be based on actual sampling times. The nemralisib pharmacokinetic parameters listed below will be determined from the plasma concentration-time data, as data permit.

Parameter	Parameter Description
AUC(0-∞)	Area under the concentration-time curve from zero time (pre-dose) extrapolated to infinite time. $AUC(0-\infty) = AUC(0-t) + C(t)/\lambda z$.
AUC(0-t)	Area under the concentration-time curve from time zero to the time of the last quantifiable concentration
%AUCex	Percentage of AUC(0-∞) obtained by extrapolation
Cmax	Maximum observed plasma concentration
tmax	Time to Cmax
t _{1/2}	Apparent terminal half-life. $t_{1/2} = \ln 2/\lambda z$

NOTES:

- Additional parameters may be included as required.
- λz is the terminal phase rate constant.

7.1.2. Summary Measure

The parameters for treatment comparisons are AUC(0-∞), AUC(0-t), Cmax, tmax and t_{1/2} for nemralisib.

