## 4. OBJECTIVES AND ENDPOINTS

Objectives	Endpoints
Primary 
 
To characterize the effect of repeat oral dosing of itraconazole on the pharmacokinetics of a single inhaled dose of nemralisib in healthy participants
 
	
 
AUC(0-∞), AUC(0-t), Cmax, tmax , t1/2
 

Secondary 
 
To investigate the safety and tolerability of single inhaled dose of nemralisib, when dosed alone and concomitantly with itraconazole, in healthy participants
 
To investigate the pharmacokinetics of itraconazole and hydroxy-itraconazole when co-administered with nemralisib
 
	
 
Adverse events (AE), clinical laboratory values, vital signs, electrocardiogram (ECG) and spirometry
 
AUC(0-∞), AUC(0-t), Cmax, tmax, t1/2
 

AUC(0-∞) Area under the concentration-time curve from time zero (pre-dose) extrapolated to infinite time, AUC(0-t): Area under the plasma concentration versus time curve from time zero to t, Cmax; maximum observed plasma concentration, tmax : time to Cmax, t1/2: Terminal phase half-life

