### 10.3.1. Pharmacokinetic Analyses

All PK analyses will be performed on the Pharmacokinetic Population.

Endpoint	Statistical Analysis Methods
Primary	
Plasma nemiralisib concentration-time data will be analysed by non-compartmental methods using WinNonlin. Calculations will be based on the actual sampling times recorded during the study.
 
From the plasma concentration-time data, the following pharmacokinetic parameters will be determined for both Day 1 in period1 and Day 5 in period 2, as data permit: maximum observed plasma concentration (Cmax), time to Cmax (Tmax), area under the plasma concentration-time curve [AUC(0-t) and AUC(0-∞)], terminal half life (t1/2) and the percentage of extrapolation for AUC(0-∞).
 
Pharmacokinetic concentration data will be presented in graphical and/or tabular form.
 
Derived pharmacokinetic parameters will be listed [subjects with greater than 20% extrapolated AUC (0-∞) will be highlighted] and descriptive statistics (n, arithmetic mean, SD, 95% CI, minimum, median and maximum) will be calculated for all pharmacokinetic parameters by treatment.
 
In addition, for loge-transformed variables the geometric mean with associated 95% CI, SD on loge-scale and between subject coefficient [%CVb (100 * √(exp(SD2) - 1))] will be provided, where the SD is the standard deviation of loge transformed data.
 
To estimate the ratio of exposure of nemiralisib administered alone and co-administered following repeat doses of itraconazole, mixed effects analyses will be performed for both loge transformed Cmax and loge transformed AUC(0-∞). The geometric mean ratios will be provided along with 90% confidence intervals and the mean squared error (MSE).

Secondary	
Plasma itraconazole concentration-time data and PK parameters [Cmax, Tmax, AUC(0-t), AUC(0-∞) and t1/2] for both Day 1 (first dose of itraconazole) and Day 5 (5th Day of dosing Itraconazole or steady state) in period 2, will be analysed, listed and summarised as described for nemiralisib.
 
No formal statistical analysis will occur.

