7.1.5.1. Statistical Methodology Specification

The following pharmacokinetic statistical analyses for nemoralisib will only be performed if sufficient data is available (i.e. if participants have well defined plasma profiles). If $AUC(0-\infty)$ is not calculable for more than 50% of subjects in the PK population in each period, $AUC(0-t)$ will also be analysed for nemoralisib as described below.

Endpoint / Variables

 • $AUC(0-\infty)$ for nemoralisib • C_{max} for nemoralisib
Model Specification

 • The parameters $AUC(0-\infty)$ and C_{max} will be \log_e transformed and analysed separately using mixed effects models. • Treatment Group will be fitted as a fixed effect and subject as a random effect. • The MIXED procedure in SAS will be used with the following options:- 
 ○ The Kenward and Roger method for approximating the denominator degrees of freedom to correct for bias in the estimated variance-covariance. • Nemoralisib co-administered with itraconazole will be compared to nemoralisib administered alone.
Model Checking & Diagnostics

 • Distributional assumptions underlying the models used for analysis will be examined by obtaining box plots and normal probability plots of the studentised residuals and plots of the residuals versus the fitted values (i.e. checking the normality assumption and constant variance assumption of the model respectively) to gain confidence that the model assumptions are reasonable.
Model Results Presentation

 • For each PK parameter:- 
 • Adjusted geometric means and 90% confidence intervals (CI) for each treatment group and standard error (\log_e scale).

- Point estimates and associated two-sided 90% confidence intervals for the ratio of nemiralisib co-administered with itraconazole to nemiralisib administered alone (obtained by back-transforming estimates and 90% CIs for the treatment differences from the statistical model on the \log_e scale) and standard error (\log_e scale).
- The mean squared error (MSE) will also be presented.

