2.8.	PK	PK03	Summary of Untransformed Derived Hydroxy Itraconazole Plasma Pharmacokinetic Parameters (Period 2)	
Don't include 95% CI.
 
Still include treatment group as a variable.
 
Include variable 'day'.
 
If any NC values, include n* column and add footnote: 'NOTE: n*=number of NC values'.
 
Include footnote: 'Nemiralisib was administered on Day 5 of Period 2.'
	SAC
2.9.	PK	PK05	Summary of Log-transformed Derived Hydroxy Itraconazole Plasma Pharmacokinetic Parameters (Period 2)	
Include all parameters except %AUCex and tmax
 
Still include treatment group as a variable.
 
Include variable 'day'.
 
If any NC values, include n* column and add footnote: 'NOTE: n*=number of NC values'.
 
Include footnote: 'Nemiralisib was administered on Day 5 of Period 2.'
	SAC
2.10.	PK	Non Standard PK_T1	Summary of Statistical Analysis of Derived Nemiralisib Plasma AUC(0-inf) and Cmax	
AUC(0-inf) and Cmax only (unless AUC(0-t) also analysed)
 
Include MSE
 
Include n* and footnote (in shell) if there are any NC values
	SAC

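### SAP 7.1.2 names nemiralisib t1/2 and tmax for treatment comparison, but no within-participant contrast or interval is planned for either

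*SAP*

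**What the plan says.** Protocol section 4 gives the primary endpoints as "AUC(0-∞), AUC(0-t), Cmax, tmax , t 1/2", and SAP 2.2 repeats them. SAP 7.1.2, headed Summary Measure, carries all five forward: "The parameters for treatment comparisons are AUC(0-∞), AUC(0-t), Cmax, tmax and t_{1/2} for nemralisib".

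The sections that specify the estimation are narrower:

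- SAP 2.4: "For AUC(0-∞) and Cmax, point estimates and corresponding two-sided 90% confidence intervals (CIs) will be constructed for the ratio of the geometric means".
- SAP 7.1.5.1 lists AUC(0-∞) and Cmax as the variables to be modelled on the loge scale: "Treatment Group will be fitted as a fixed effect and subject as a random effect". AUC(0-t) "will also be analysed for nemoralisib as described below" only if AUC(0-∞) cannot be calculated for more than half of the PK population in each period.
- The programming note for Table 2.10 (SAP 11.8.5) reads "AUC(0-inf) and Cmax only (unless AUC(0-t) also analysed", and Figures 2.9 and 2.10 carry the same limit.
- Protocol 10.3.1 plans mixed-effects analyses for the same two parameters and no others.

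The remaining parameters are handled descriptively. Table 2.4 summarises all nemiralisib parameters untransformed, by treatment. Table 2.5 does so on the log scale and leaves out %AUCex and tmax. Listing 37 gives each participant's derived values.

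**The concern.** A reader of SAP 7.1.2 expects a treatment comparison for five parameters and finds one specified for two, or three if the AUC(0-t) condition is met. In the usual case three primary endpoints have no planned contrast.

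Half-life is the one that matters most. The study asks whether CYP3A4 inhibition slows nemiralisib clearance. The design invests in the elimination phase: Protocol 5.5 says the long half-life sets the sampling length, extends sampling to 144 h in Period 2, and continues itraconazole after the nemiralisib dose so that inhibition lasts. A change in t1/2 helps to tell slower elimination from a change in absorption.

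The by-treatment summaries do not supply the missing interval. Protocol 5.4 has each participant serve as his or her own comparator, and two separate per-treatment intervals ignore that. They may also describe different people. The PK population needs only one nemiralisib dose and one analysed sample (SAP section 4), about 20 are enrolled to obtain about 16 evaluable, and t1/2 is derived only where the data allow. If the contrast is left to be calculated after the data are seen, its form is open to choice.

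**Working it through.** **1. Promise against delivery for each primary endpoint**

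| Parameter | Named in SAP 7.1.2 | Ratio and 90% CI planned | Other planned output |
|---|---|---|---|
| AUC(0-∞) | yes | yes | Tables 2.4, 2.5; Listing 37 |
| Cmax | yes | yes | Tables 2.4, 2.5; Listing 37 |
| AUC(0-t) | yes | only under the condition in 7.1.5.1 | Tables 2.4, 2.5; Listing 37 |
| t1/2 | yes | no | Tables 2.4, 2.5; Listing 37 |
| tmax | yes | no | Table 2.4; Listing 37 |

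No section, table or figure in either document contrasts t1/2 or tmax between treatments.

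**2. The plan's own precision figures**

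Inputs from Protocol 10.1: total SD (loge) 0.382 for AUC(0-∞) and 0.411 for Cmax; correlation 0.253 and 0.302; n = 16.

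- Within-subject SD = total SD × √(1 − ρ): 0.382 × √0.747 = 0.330; 0.411 × √0.698 = 0.343. Both match the protocol.
- 90% CI = ratio × exp(± t × SD × √(2/16)), where √(2/16) = 0.354.
- With 30 df (t = 1.697) and ratio 1: AUC(0-∞) 0.82 to 1.22; Cmax 0.81 to 1.23. These are the protocol's figures.
- With 15 df (t = 1.753), which fits 16 complete pairs: 0.815 to 1.227 and 0.808 to 1.237, slightly wider.

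No precision is stated for t1/2 or tmax.

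**3. The same formula applied to t1/2**

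The documents give no SD for t1/2, so the range below is an assumption (n = 16, 15 df).

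| Assumed within-subject SD (loge) | 90% CI as a multiple of the t1/2 ratio |
|---|---|
| 0.10 | 0.94 to 1.06 |
| 0.20 | 0.88 to 1.13 |
| 0.30 | 0.83 to 1.20 |
| 0.40 | 0.78 to 1.28 |

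Up to an SD of about 0.33 the interval is no wider than the one already accepted for AUC(0-∞).

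**4. What ignoring the pairing costs**

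Unpaired SE divided by paired SE = 1/√(1 − ρ). At the documents' 0.253 for AUC(0-∞) this is 1/0.864 = 1.16, an SE about 16% too large. At 0.6, an assumed value, it is 1/0.632 = 1.58. No correlation is given for t1/2.

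**5. How well λz could be determined**

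Protocol 5.5 gives a half-life of about 40 h for nemiralisib alone, so 144 h of sampling spans 144/40 = 3.6 half-lives. If half-life rose to 80 h or 120 h (assumed), the span would be 1.8 or 1.2. The t1/2 ratio would be least certain when the interaction is largest.

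**The case against.** The strongest reply is that the estimation plan is coherent and one sentence is loose. The precision calculation, Protocol 10.3.1, SAP 2.4 and 7.1.5.1, and the table and figure specifications agree that AUC(0-∞) and Cmax carry the contrast. SAP 2.1 declares no departure from the protocol, which never planned a t1/2 or tmax contrast. SAP 7.2.2 uses the same sentence for itraconazole and hydroxy-itraconazole, although 7.2.4 plans no formal analysis there. This suggests template text, and a section on summary measures need not promise a model. That explains the mismatch but leaves it in place: the SAP still names t1/2 for comparison and specifies none.

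Three stronger readings are tempting, and the documents do not support them.

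- *The effect on half-life is never estimated.* Table 2.5 reports geometric mean t1/2 for each treatment, and dividing the two gives a ratio. With complete pairs this is the model's point estimate. Listing 37 allows a paired calculation after the fact. Only the pre-specified contrast and its interval are missing.
- *The AUC(0-∞) ratio rests on unexamined extrapolation.* %AUCex is derived and summarised, and values above 20% are flagged (SAP 7.1.1.2, 7.1.5, Table 2.4, Listing 37). SAP section 9 plans population or physiologically based modelling if clearance falls so far that sampling is inadequate. %AUCex measures extrapolation more directly than a t1/2 ratio does.
- *tmax needs its own interval.* Protocol 5.5 reports tmax at the first sample, 5 minutes after dosing, and the next sample is at 30 minutes. Many paired differences may be zero, so an interval would add little.

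**Conclusion.** The inconsistency stands: five primary endpoints are named for treatment comparison and two are reliably given one. The material loss is the absence of a pre-specified within-participant t1/2 ratio with an interval. Its consequence is limited. No hypothesis is tested, the AUC(0-∞) and Cmax ratios do not change, and a crude t1/2 ratio remains available.

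Adding the t1/2 contrast is a worthwhile, inexpensive improvement and does not correct any error in the main result. Its likely precision rests on an assumed SD. The statement that separate summaries overstate the uncertainty by about 16% rests on borrowing the AUC(0-∞) correlation. If half-life is greatly prolonged, λz will be poorly determined and the interval should be read with that in mind.

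**What to change.** 1. In SAP 7.1.5.1, add loge t1/2 for nemiralisib to the endpoint list, with the same mixed model, ratio and 90% CI. Extend SAP 2.4 to match and record the addition in SAP 2.1.
2. Show the t1/2 ratio in Table 2.10 and Figure 2.10, amending their titles and programming notes.
3. Add a note that the t1/2 ratio is to be read alongside %AUCex, because λz will be imprecise if half-life is much prolonged relative to 144 h of sampling.
4. Reword SAP 7.1.2 so that AUC(0-∞), Cmax and t1/2 are compared by model, while tmax, and AUC(0-t) when its condition is not met, are compared descriptively. A paired median difference for tmax is optional.

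The cost is SAP wording and one further run of a model already specified. It needs no new participants, samples or data. There is no error-rate cost, since no hypotheses are tested (Protocol section 10) and no multiplicity adjustment is planned (SAP 5.3). The one downside is a t1/2 interval that may be imprecise if half-life is greatly prolonged. The change should be made before database freeze, so that the form of the contrast is fixed in advance.
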